Section 2: Introduction

Background and rationale

Item 7:

The product-line of logistics wholesale companies are characterized by a low level of automation due to the big variety of goods, making them highly dependent on manual handling of materials (Danko & Straka, 2022). This is accompanied by strenuous tasks comprising heavy workloads, awkward postures, and repetitive movements (Glock et al., 2021; Skals et al., 2020). These tasks are considered as risk factors contributing to work-related musculoskeletal disorders (WMSDs) (Govaerts et al., 2021; Katz, 2006). Exoskeletons have been proving beneficial in terms of decreasing the muscular activity of target areas of the body during physical activity (Nussbaum et al., 2020; Theurel & Desbrosses, 2019). Thus, occupational exoskeletons represent potential benefits in terms of reducing the musculoskeletal loads during manual materials handling, and thereby reducing the risk of WMSDs. In a previous study, we report a 13-20% reduction in peak back muscle activity when wearing a back-supporting exoskeleton during similar work tasks (Schröder Jakobsen et al., 2024).

However, literature still claims a lack studies investigating the long-term effects of wearing an exoskeleton on the biomechanics of the user (Crea et al., 2021; Howard et al., 2020; Kranenborg et al., 2023; Theurel & Desbrosses, 2019). Thus, this randomized controlled trial investigated the biomechanical changes after a 24-week period of using a back-supporting exoskeleton (BSE) for manual order picking tasks. Furthermore, it included data on the changes in musculoskeletal discomfort, acceptance of the exoskeleton, and perceived effort and work intensity of warehouse workers.

Objectives

Item 8: Description of objectives and hypothesis

The primary objective was to examine alterations in biomechanical parameters after 24 weeks of practical application of a back support exoskeleton (BSE). Furthermore, secondary aims encompassed the

investigation of changes in user acceptance, exoskeleton comfort levels, perceived exertion during tasks, and incidences of musculoskeletal discomfort following prolonged utilization of the exoskeleton device.

Hypothesis:

Based on established literature, we hypothesized that a duration of 24 weeks employing the BSE will yield positive impact on user biomechanics characterized by diminished back muscle activity and decreased knee flexion indicating a more stoop lifting technique (Diamond-Ouellette et al., 2022; Poggensee & Collins, 2021; Schröder Jakobsen et al., 2024). Furthermore, we hypothesized that prolonged utilization of the BSE will increase exoskeleton comfort and acceptance among users, concomitant with a reduction in perceived work intensity and occurrences of musculoskeletal discomfort, due to the anticipated mitigation of biomechanical load (Kazerooni et al., 2019; Schröder Jakobsen et al., 2024).

Section 3: Trial methods

Trial design

Item 9: Description of trial design

This trial was designed as a randomized controlled parallel intervention trial. Exoskeleton usage was allocated to the participating workers in a 1:1 ratio. The workers were randomized to intervention and controls. The intervention group was allocated a BSE for a 24-week period to perform their work tasks, while the control group performed their work tasks as normal for the same period. The primary endpoint was at the 24-week post-test.

Randomization

Item 10: Randomization details

The randomization was performed by an external blinded researcher not involved in data collection or assessments. After informed consent and baseline assessments had been conducted, the participants were randomly assigned to either intervention or control group using stratified randomization. Sex, work experience, and previous experience issues of low back-pain were used as strata.

Sample size

Item 11: Full details of sample size calculations

A priori sample size calculation for a repeated measure, within-between interaction design was conducted to estimate the required sample size to achieve a power of 80%. The calculation was based on effect sizes previously reported on training effects of the present BSE on muscular activity from SEMG erector spinae measurements ($\eta^2 \geq .370$) (Schröder Jakobsen et al., 2024). A two-sided significance level at .05 was set and revealed that a total minimum of 18 workers was required resulting in an actual power of .838. To account for a 10% drop-out, a total of 20 workers (10 per group) were enrolled.

Framework

Item 12: Description and hypothesis testing framework

Primary outcomes (biomechanical measurements) were evaluated in a within-between interaction framework, hypothesizing that the workers would experience a reduction in muscular activity and changed kinematics when using the BSE, and further that the reduction will increase from baseline to post-test in line with previously reported training effects (Diamond-Ouellette et al., 2022; Poggensee & Collins, 2021;

Schröder Jakobsen et al., 2024). Secondary outcomes, were evaluated in a superiority framework, hypothesizing that workers using the BSE would witness a reduction in musculoskeletal discomfort and perceived work intensity, and increased acceptance of comfort in relation to BSE usage. A significance level of .05 will set.

Statistical interim analysis and stopping guidance

Item 13:

No interim analysis was planned, and no adjustment of significance level was made. No stopping rules was defined a priory.

Timing of final analysis

Item 14:

The analysis of primary, secondary, and other outcomes was conducted collectively when all workers had completed the test session post the 24-week intervention/control period. The 24-week intervention was expected to finish in April 2024. Biomechanical data from baseline and post-test, and questionnaire data from all the data points (baseline + 4-, 8-, 12-, 16-, 20-weeks, and post-test) were be included in the analysis.

The analysis of the primary, pre-specified secondary, and other outcomes (item 26) will be reported in the primary publication. The remaining outcomes will be reported in the secondary publication.

Timing of outcome assessment

Item 15:

Biomechanical outcomes (surface electromyography (SEMG) and kinematics) and perceived effort will be evaluated at baseline and post-tests. The questionnaire assessed outcomes (perceived work intensity, exoskeleton comfort and acceptance, and musculoskeletal pain) will be evaluated continuously during the intervention period at four-week intervals ending at post-test. Further details can be found at the published study protocol (NCT05890300).

Section 4: Statistical principles

Confidence intervals and p-values

Item 16: Level of statistical significance

All conducted statistical tests will be two-sided and evaluated by a significance level of 5% (i.e., $p = .05$).

Item 17: Description of planned adjustment for multiplicity

To take precaution for multiplicity, multivariate statistical tests will be conducted to reduce the number of analyses ran, and thus the family-wise error rate. Additionally, Bonferroni corrections will be conducted to reveal significant differences when more repeated measures are occurring, which is considered a conservative approach in terms of reducing family-wise errors (Robert, 2020).

Item 18: Confidence intervals

The presented confidence intervals will be 95% and be two-sided.

Adherence and protocol deviation

Item 19a: Definition of adherence to interventions

Adherence will be defined as the workers of the intervention group compliance to BSE usage during the 24-week period. The protocol consists of a 5-weeks familiarization period consisting of progressive usage of the BSE (Schröder Jakobsen et al., 2023), followed by 19 weeks of minimum 18-hours of BSE usage per week. Adherence is self-registered day-by-day by the individual worker and monitored by the principal researcher.

Item 19b: Description of how adherence to intervention will be presented

Adherence to the intervention will be reported as weekly reported hours of BSE usage during the full 24-week period. Weekly hours of BSE usage will be reported at both individual and group level.

Item 19c & 19d: Definition of protocol violation for the trial and how they will be presented

It is specified as an exclusion criterion if workers resigns / get laid off during the intervention period.

Analysis populations

Item 20: Definition of analysis populations

The analysed population corresponded to the workforce of a specific department at a Danish logistics company. The department consists of a total workforce of approx. 70 fulltime employees. Only fulltime workers were included in the trial. Workers who should resign during the intervention period will be excluded from the analysis.

Section 5: Trial population

Screening data

Item 21: Reporting of screening data

The recruitment period will be showcased from start to end alongside the total number of workers screened for eligibility.

Eligibility

Item 22: Summary of eligibility criteria

Workers were eligible to participate in the trial if they fulfilled the inclusion criteria:

- Full-time employed at the department handling fruits and vegetables at Dagrofa Logistics A/S
- No major injuries affecting their daily work tasks
- No plans of retiring before the end of the intervention period

Study exclusion criteria were:

- Body compositions unable to fit the exoskeleton (bad fit)
- Part-time employment
- Previous low-back injuries

Recruitment

Item 23 & 24: Information to be included in CONSORT flow diagram

A CONSORT flow diagram will be displayed, including the following information:

- Number of workers assessed for eligibility throughout the recruitment period
- Number of workers not meeting the inclusion criteria's or not consenting to participate

- Number of workers eligible for inclusion
- Number of workers randomized to both arms of intervention (intervention & control)
- Number of workers included in baseline and post-test sessions
- Number of workers included in 4-, 8-, 12-, 16-, and 20-week questionnaire assessments
- Number of excluded workers and withdrawals throughout the intervention period

Baseline worker characteristics

Item 25a: List of baseline characteristics to be summarized

The workers will be described with baseline, demographic characteristics which include sex, age, height, body mass, BMI, work experience, and previously experienced low back-pain rated using a simplified version of the Nordic questionnaire (Kuorinka et al., 1987).

Item 25b: Details on how baseline characteristics will be descriptively summarized

Table 1 illustrates how the baseline characteristics will be interpreted. Continuous data will be presented as mean \pm SD if data is normally distributed and as median and range if data is non-normally distributed. Categorical data will be presented as numbers and percentages. No test for statistical significance for the baseline characteristics will be conducted in line with the recommendations by the CONSORT statement (Moher et al., 2010).

Table 1: Baseline characteristics of the workers

Characteristics	Intervention group	Control group
Age (years), mean \pm SD		
Sex (men/women), n & %		
Height (cm), mean \pm SD		
Body mass (kg), mean \pm SD		
Body mass index (kg/m ²), mean \pm SD		
Work experience (years), mean \pm SD		
Previously experienced low back-pain (0-10 index), mean \pm SD		

Section 6: Analysis

Outcome definitions

Item 26: Specifications of outcome and timings

Table 2 specifies the measured outcomes, the timing of assessment, and the analysis methods. Further detailed descriptions can be found in the open access protocol (NCT05890300).

Table 2: Overview of primary, secondary, and other outcomes.

	Instrument for assessment	Timing for assessment	Analysis method
Primary outcome – reported in primary publication			
Changes in muscular activity of the back i) with/without BSE,	Surface electromyography (SEMG) analysis of erector spinae longissimus and	Baseline and 24-week post-test	Two-way Repeated measures multivariate analysis of variance

and ii) pre/post the 24-week intervention. Based on standardized work tasks performed during test sessions.	lower trapezius, including normalization to maximum isometric voluntary contraction. The analysis will include the 10 th , 50 th and 90 th percentile of the SEMG amplitude.		(2RM-MANOVA)
Changes in kinematical pattern of the back and knee joints i) with/without BSE, and ii) pre/post the 24-week intervention. Based on standardized work tasks performed during test sessions.	Inertial measurement unit based, full-body motion capture analysis. The analysis will include the 10 th , 50 th and 90 th percentile of the back forward bending and rotation (cumulative T8-S1) and knee flexion/extension joint angles.	Baseline and 24-week post-test	2RM-MANOVA
Secondary outcome – reported in primary publication			
Changes in perceived effort i) with/without BSE, and ii) pre/post the 24-week intervention. Based on standardized work tasks performed during test sessions.	Assessed using Borg Category-Ratio (CR) scale (0 = no effort, 10 = maximum effort).	Baseline and 24-week post-test	2RM-MANOVA
Changes in BSE comfort and performance	Assessed using a questionnaire including questions on fit and (thermal) comfort, balance, range-of-motion, safety, and perceived job performance. All questions are answered using a 10-point Likert-scale (e.g., 0 = no discomfort, 10 = most discomfort) (Kim et al., 2022).	Baseline, 4-, 8-, 12-, 16-, 20-weeks, and post-test	One-way Repeated measures multivariate analysis of variance (1RM-MANOVA)
Changes in liking of the BSE	Assessed using open-ended questions on liking: Q1: "What do you most like about the exoskeleton?", Q2: "What do you least like about the exoskeleton?", Q3: "If you could change anything about the exoskeleton, what would you change?" (Kim et al., 2022).	Baseline, 4-, 8-, 12-, 16-, 20-weeks, and post-test	1RM-MANOVA

Changes in perceived work intensity	Assessed using a questionnaire including questions on work intensity. All questions are answered using a 10-point likert-scale (0 = strongly agree, 10 = strongly disagree) (Kim et al., 2021).	Baseline, 4-, 8-, 12-, 16-, 20-weeks, and post-test	IRM-MANOVA

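### SAP Item 11: the printed pair of 18 workers and power .838 does not come from an eta-squared of .370; it matches .370 entered as Cohen's f

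*SAP*

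**What the plan says.** SAP Section 3, Item 11 describes the calculation as follows: "A priori sample size calculation for a repeated measure, within-between interaction design was conducted", with a target power of 80%. The effect size is an eta-squared of at least .370, taken from "effect sizes previously reported on training effects of the present BSE on muscular activity from SEMG erector spinae measurements". On the error rate it says "A two-sided significance level at .05 was set". The result is "a total minimum of 18 workers was required resulting in an actual power of .838", and then "To account for a 10% drop-out, a total of 20 workers (10 per group) were enrolled". Item 9 gives 1:1 allocation to two groups.

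Item 11 does not say how eta-squared was converted to the program's effect-size input, how many repeated measurements were assumed, or what correlation between them was used. Table 2 (Item 26) shows the primary outcomes measured at baseline and at the 24-week post-test, each with and without the exoskeleton.

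**The concern.** Power is a deterministic output. Once the design, effect size, alpha and N are fixed, it takes one value for each convention. Sample-size programs ask for Cohen's f, or a variant of f derived from partial eta-squared, so eta-squared must be converted first. An eta-squared of .370 is f = .766; an f of .370 is an eta-squared of only about .12. If one was entered as the other, the effect named in Item 11 is not the effect the trial was sized for.

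At stake is how the result is read. Readers will set the findings from 18 to 20 workers against a stated 84% power for a stated effect. That statement should be reproducible and correctly labelled. It should also refer to the contrast that the calculation tests, which is the group difference in change.

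**Working it through.** **Inputs from the SAP.** k = 2 groups, 1:1 (Item 9); within-between interaction, alpha .05, target power .80, eta-squared .370, N = 18, power .838 (Item 11).

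**Assumed, because Item 11 does not state them.** m = 2 measurements (baseline and post-test), correlation rho = .5 unless varied, sphericity (epsilon = 1).

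**Test.** Noncentral F with df1 = (k−1)(m−1) = 1 and df2 = (N−k)(m−1) = N−2. At N = 18, df2 = 16 and the critical F is 4.494.

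**Conversions.**
- Eta-squared .370: f² = .370/.630 = .587, f = .766.
- f = .370: f² = .1369, eta-squared = .1369/1.1369 = .120.

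**Reproducing the printed pair.** Take f = .370 and lambda = N f² m/(1−rho).
- N = 16: lambda = 16 × .1369 × 2/.5 = 8.762, power .786.
- N = 18: lambda = 18 × .1369 × 2/.5 = 9.857, power .8381.

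The smallest even N reaching .80 is 18, and the power agrees with the SAP to three decimals. The drop-out step also reproduces: 18/.90 = 20.

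**Treating .370 as eta-squared (f² = .587), m = 2.**

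| Convention | Lambda at N = 18 | Smallest even N (power) | Power at N = 18 |
|---|---|---|---|
| lambda = N f² m/(1−rho), rho = .5 | 42.29 | 8 (.947) | about 1.00 |
| SPSS-type partial eta-squared, lambda = f²(N−k) | 9.397 | 18 (.8205) | .8205 |
| lambda = f² N | 10.571 | 16 (.813) | .862 |

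None prints 18 with .838. In the first convention no correlation can rescue it. Power .838 at N = 18 needs lambda = 9.855, so 1−rho = 18 × .587 × 2/9.855 = 2.145 and rho = −1.15, which is impossible. Counting four measurements per worker (with and without the device, before and after) does not help either: the SPSS-type convention then gives N = 10.

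**Dependence on the unstated correlation.** With f = .370, m = 2 and N = 18, power is .55, .70, .84 and .97 for rho = 0, .3, .5 and .7. With m = 4 and rho = .5 it is .96.

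**What the design can detect.** With n = 9 per arm and d the group difference in mean change divided by the SD of change, lambda = (n/2)d² = 4.5 d².
- Power .838: d = √(9.857/4.5) = 1.48.
- Power .80: lambda = 8.907, d = √(8.907/4.5) = 1.41.
- SPSS-type reading (power .8205): d = √(9.397/4.5) = 1.45.

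The detectable difference is therefore about 1.4 to 1.5 SD of change whichever of these readings applies.

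**Conditional check on the source effect.** Assume that eta-squared .370 was a one-group pre/post effect, that the standardised change is therefore .766, and that controls do not change. Then lambda = 4.5 × .587 = 2.643 and power with 9 per arm is .333.

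**The case against.** The strongest defence is that 18 workers is compatible with the stated effect. Under the SPSS-type convention, a standard variant, eta-squared .370 gives power .760 at N = 16 and .8205 at N = 18, so 18 is exactly the minimum. This stands: the number of workers alone does not reveal an error. It does not rescue the printed power, because .8205 is not .838 and another input matches .838 to three decimals.

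It is also fair that the f entry is an inference. It needs two measurements and a correlation of .5, and Item 11 states neither. The match is strong evidence, not proof.

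A reader might infer that the trial is underpowered for the effect it names. The SAP does not support that. If .370 is an interaction eta-squared, power at N = 18 with two measurements is .82, .86 or about 1.00. If f = .370 was used, the trial was sized for a smaller effect than Item 11 states, which is conservative.

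A reader might also take the 33% as the trial's true power. That rests on an assumption about a cited study that is not at hand. Item 11 speaks only of training effects and does not say whether the earlier study had a control group or which contrast the statistic describes. Finally, nothing in the SAP treats non-significance as absence of effect, and Item 18 plans 95% confidence intervals, so misreading of a null result is a risk and not a planned step.

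**Conclusion.** As written, the effect size and the power in Item 11 do not belong together. Treating .370 as eta-squared gives .8205, .862 or about 1.00 at N = 18 under the conventions tried, against a printed .838. Entering .370 as Cohen's f, with two measurements and correlation .5, gives N = 18 and .8381. A mix-up of eta-squared and f is the likeliest cause, subject to the sponsor's confirmation of those inputs.

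The defect lies in a stated figure and its label. The number enrolled is not shown to be wrong, and power for an interaction eta-squared of .370 is at least .82 (two measurements assumed). One question remains open: Item 11 takes the effect from an earlier training effect and applies it to a between-group difference in change, without saying that the two are the same kind of quantity. If they are not, the stated power does not apply to the contrast being tested.

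**What to change.** Amend Item 11 as follows.

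1. Confirm and state the effect-size metric and conversion convention, the number of measurements and the assumed correlation.
2. Correct whichever is wrong: the label (f = .370, eta-squared about .12) or the power (for example .82 under the SPSS-type convention).
3. Give the detectable effect with 9 per arm: a group difference in change of about 1.48 SD of change at 84% power, or 1.41 SD at 80%.
4. Say whether the earlier training effect was a within-worker change or a between-group difference in change. If it was within-worker, restate the power for the between-group contrast together with its assumptions. The figure of about 33% holds only for a standardised change of .766 with no change in controls, and should not be entered unless the source supports that.

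The cost is a few sentences of SAP wording. No extra workers are needed, and the tests and alpha stay as they are. The downside is a stated figure that is less favourable or carries a different label.

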The remaining secondary outcomes will be assessed for normality and sphericity using an approach similar to the primary outcomes. However, a different statistical analysis will be conducted due to the difference in factors. A one-way repeated measures multivariate analysis of variance (1RM-MANOVA) with timepoints (baseline, 4-, 8-, 12-, 16-, 20-weeks, and post-test) as the independent factor and comfort, performance,

liking, work intensity, and musculoskeletal discomfort as dependent outcomes will be used for assessment. If any significant change is detected, an additional post hoc (Bonferroni) analysis will be performed.

The primary outcomes (including perceived effort) will be reported in figures including with /without BSE usage measures from baseline and post-test. In this case mean and individual values from both groups will be reported. The remaining secondary outcomes will be reported in figures including data from all time points (baseline, 4-, 8-, 12-, 16-, 20-weeks, and post-test). Similarly, mean, and individual values from both groups will be reported.

The individual BSE usage will be depicted in a graph for the workers included in the intervention group. This will include week-to-week reporting of individual BSE usage and group mean. The BSE usage will not be statistically analysed.

The secondary publication will focus on the potential changes in productivity of the worker when using the BSE. It will include a regression analysis between individual productivity of the worker, and the hours using the BSE. Additional outcomes will also be included in the publication, i.e., monitoring of temporal changes in musculoskeletal discomfort during the intervention period. The coherence between productivity and BSE usage will be depicted in scatter plots.

Missing data:

Item 28: Reporting and assumptions/statistical methods to handle missing data (e.g., multiple imputation)

If any worker was excluded from the trial initial to the post-test (i.e., due to resignation), none of the excluded worker's data will be included in the analysis. Number of data points available in each group at any timepoint will be displayed in the primary publication. Workers violating the protocol by using the BSE less than intended, will not be excluded from the analysis. However, the effect of this potential issue will be handled in additional analyses (see below).

Additional analyses

Item 29:

The following additional analyses may be added:

- Correlations between demographics and BSE usage to analyse the potential effects of demographics on exoskeleton acceptance.
- Cluster analysis of the effect of BSE usage on primary outcomes to analyse potential differences between workers in the intervention group with high and low adherence to BSE usage.

Harms

Item 30: Sufficient detail provided on summarizing harms

This study is designed to identify any harms or adverse events that may occur during the intervention. Self-reported changes in musculoskeletal discomfort and perceived work intensity will be monitored during the trial (see table 2). Additionally, the workers will at each timepoint be able to pass their individual feedback on the BSE, in term of what they 'least like', 'most like', and if they would change anything about the exoskeleton, in an open-ended questionnaire. Adverse events will be descriptively summarized for both groups and reported in the primary publication.

Statistical Software

Item 31: Details of statistical package used for the analysis

The statistical package IBM Corp. 2022. IBM SPSS Statistics for windows, Version 27.0. Armonk, NY: IBM Corp. was used for data management and analysis.

References

Item 32: Data Management

All the data will be stored in accordance with the Danish Personal Data Protection Act and other relevant Danish legislation. Biomechanical data is recorded in the original software file format (Noraxon and mvnx, respectively) and later exported to Matlab (MAT) format. Questionnaire data is recorded in hard copy during the outcome assessments and later noted in Excel spreadsheets. The main data set will not contain any personal information. Additionally, no personal information of the participants will be shared by the principal investigator and will be stored securely for his eyes only.

As mentioned, the analyses described in the present SAP will be performed by the principal investigator and be the basis of all primary and secondary outcomes. However, to avoid the risk of misleading interpretation, a blinded interpretation will be performed by the members of the research team (all but [name]). The principal investigator will code the randomized groups as “group A” and “group B” before passing the statistical results to the blinded member. Thereby, the interpretation of the results will be blinded to allocation of BSE usage. The blinded members will then decide on two different interpretations of the results: one in which group A refers to the intervention group and group B to the control group, and one vice versa. The interpretations will be registered in a document titled “EXO4MMH trial: Blinded data analyses interpretation statement”. After registration of the different interpretation, the randomization will be broken, and the correct interpretation will be chosen as prescript to the primary publication (Järvinen et al., 2014).

References

- Danko, A., & Straka, M. (2022). Exoskeletons-Robotic Suits Improving Work in Logistics. *Acta Logistica*, 9(4), 405-410.

- Glock, C. H., Grosse, E. H., Neumann, W. P., & Feldman, A. (2021). Assistive devices for manual materials handling in warehouses: a systematic literature review. *International Journal of Production Research*, 59(11), 3446-3469.

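### Item 27 tests the questionnaire outcomes with a time-only, seven-visit omnibus test that gates unspecified Bonferroni comparisons; it names no baseline-to-24-week contrast and no comparison between arms

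*SAP*

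**What the plan says.** Item 27 enters comfort, performance, liking, work intensity and musculoskeletal discomfort together in a one-way repeated measures MANOVA. Its only independent factor is time, with seven levels: baseline, weeks 4, 8, 12, 16 and 20, and post-test. The follow-up rule is "If any significant change is detected, an additional post hoc (Bonferroni) analysis will be performed". Item 17 adds that "Bonferroni corrections will be conducted to reveal significant differences when more repeated measures are occurring". Neither item says which visits are compared, how many comparisons there are, or what the divisor is. Group is not a factor in this model.

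The questions are stated elsewhere. Item 8 lists among its secondary aims "incidences of musculoskeletal discomfort following prolonged utilization of the exoskeleton device" and hypothesises more comfort and acceptance, with less work intensity and discomfort, after prolonged use. Item 12 puts the secondary outcomes in a superiority framework for workers using the exoskeleton. Item 9 says "The primary endpoint was at the 24-week post-test". Item 15 has the questionnaires assessed every four weeks up to the post-test, and no sentence names week 24 as the single time point for them.

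**The concern.** The omnibus null is that all seven visit means are equal. Rejecting it shows that some visits differ. It does not show that discomfort or work intensity is lower, or comfort higher, at the end of 24 weeks, and without an arm factor it does not show that exoskeleton users differ from controls.

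The 24-week change is reached only through the gate, and then at a Bonferroni level that the SAP does not fix. The level is .05/21 = .0024 if all pairs of visits are compared and .05/6 = .0083 if each visit is compared with baseline. Many of the 21 pairs, such as week 8 against week 16, match no stated hypothesis, yet each would lower the level for the contrast that does.

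Two things are at stake. With 20 workers, a sizeable 24-week change could go undetected. And because the family of comparisons is open, the questionnaire conclusion in the primary publication could depend on a choice made after the data are seen.

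**Working it through.** **1. The plan's own figure.** The only power calculation is for muscle activity: "The calculation was based on effect sizes previously reported on training effects of the present BSE on muscular activity from SEMG erector spinae measurements", with the result "a total minimum of 18 workers was required resulting in an actual power of .838". For a within-between interaction with k=2 groups, m=2 times, correlation .5 (assumed) and f=.370:
- λ = f²·N·m/(1−ρ) = .370² × 18 × 2/.5 = 9.86, with 1 and 16 df, gives power .838. The figure reproduces, and 18/.90 = 20 enrolled.
- The match treats .370 as Cohen's f although the SAP labels it η². The sponsor should confirm this separately.
- None of it carries over to the questionnaires, for which no effect size, SD or correlation is given. Everything below is therefore assumption.

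**2. Number of comparisons.** Seven visits give 7×6/2 = 21 pairs, or 6 comparisons with baseline.

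**3. Bonferroni step alone.** Assume one outcome with SD 1 at each visit and correlation .6 between visits. The SD of change is √(2(1−.6)) = .894. The noncentrality is (change/.894)·√N, and power comes from the noncentral t with N−1 df. The changes are chosen so that the single contrast has about 80% power.
- N=20 (both arms pooled, as the time-only model implies), change 0.6 SD: noncentrality 3.00.
- N=10 (exoskeleton arm only), change 0.9 SD: noncentrality 3.18.

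| Level for the 24-week contrast | N=20 | N=10 |
|---|---|---|
| .05, single contrast | 81% | 81% |
| .05/4 = .0125 | 60% | 55% |
| .05/6 = .0083 | 53% | 48% |
| .05/21 = .0024 | 35% | 27% |

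**4. Gate plus Bonferroni.** This was simulated with a Greenhouse-Geisser omnibus test at .05, under linear, plateau and late trajectories:
- N=20: about 33-34% (21 pairs) or 49-51% (6). Losses: 81−34 = 47 to 81−33 = 48, and 81−51 = 30 to 81−49 = 32 points.
- N=10: about 25% or 43-44%. Losses: 81−25 = 56, and 81−44 = 37 to 81−43 = 38 points.

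Comparing steps 3 and 4, most of the loss comes from the divisor and only a few points from this univariate gate.

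**5. Arm contrast.** For a 10 v 10 comparison of change with 80% power at .05, the Bonferroni step alone leaves 33% (21 tests) or 52% (6 tests). Adding an arm factor while keeping the same rule does not remove the loss.

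**6. Wider assumptions.**
- Smallest loss: N=20, single-contrast power 99%, 6 comparisons, Bonferroni step only: 99−93 = 6 points.
- Largest loss: N=10, single-contrast power 80%, 21 pairs, Hotelling gate: 80−11 = 69 points.
- The planned gate is multivariate. A full version over five outcomes needs 5×6 = 30 contrasts against 9 (one arm) or 19 (pooled) error df and cannot be computed. An averaged version leaves 17-25% at N=10 and 22-34% at N=20 (80% case, 21 pairs).

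**7. Like-for-like comparison.** An unadjusted .05 test is not a fair comparator for a multiplicity-controlled rule. Holm's strictest step over four quantitative outcomes (comfort, performance, work intensity and discomfort, one score each) is .0125, where the contrast has about 60% (N=20) or 55-56% (N=10).
- Against 6 comparisons: 60−51 = 9 to 56−43 = 13 points gained.
- Against 21 pairs: 60−34 = 26 to 56−25 = 31 points, or about 25-31 allowing for rounding and simulation error.

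**The case against.** The strongest reply is that the SAP describes a trajectory, not a single visit. Items 14 and 15, Table 2 and the planned figures all use every time point. The 24-week endpoint in Item 9 is the primary one, and Item 8 speaks of prolonged use without naming a week. On that reading a seven-level time factor fits the assessment plan. This stands in part: week 24 is an inference for the questionnaires and needs the sponsor's confirmation. It does not rescue the rule, because a trajectory analysis would still need a named family of comparisons and, under Item 12, an arm comparison.

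Second, Item 17 chooses multivariate tests and Bonferroni deliberately and calls the latter conservative. That also stands. It is why the fair gain is the one against Holm, and why removing the gate requires a replacement.

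Three stronger readings are tempting and are not supported:
- **That power falls by a fixed 30 to 50 points.** That range depends on an assumed effect, correlation and divisor, and the SAP supplies none of them.
- **That a true 24-week change would usually be reported as not significant.** This follows only from the effect sizes assumed here; a large effect loses little.
- **That a week-4 transient during familiarization makes the omnibus test reject for the wrong reason.** If week 4 truly differs, rejecting equality is correct, and the post hoc tests and figures could locate it. The limitation is only that such a rejection does not answer the question about prolonged use.

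Finally, intermediate visits matter because Item 30 uses discomfort and work intensity to monitor harms. The fix must keep them.

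**Conclusion.** The point holds as a mismatch between test and hypothesis, together with an unspecified comparison family. Item 27 does not directly test the effects of prolonged use in Item 8 or the superiority question in Item 12. The absent arm factor is the larger part of that mismatch, and a within-worker 24-week contrast alone would not repair it.

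The loss of power is real in direction, but its size is conditional. With about 80% power for the single contrast at .05, the gated rule leaves 25-34% (21 pairs) or 43-51% (6 comparisons) at N=10-20. This assumes a univariate gate and a common correlation of .6. The like-for-like gain is the 9-13 or 25-31 points in step 7 of the working. These are secondary outcomes, so the primary biomechanical analysis is untouched, but they are reported in the primary publication and the wording should be corrected.

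**What to change.** In Item 27 and Table 2:
- Confirm that week 24 is the key time point for the questionnaires.
- For each quantitative questionnaire outcome, pre-specify one contrast, the change from baseline to the 24-week post-test, with a 95% CI and not conditional on an omnibus test. Make it between arms for discomfort and work intensity. Make it within the exoskeleton arm for comfort and performance, since controls work without the device; that contrast is not a randomised comparison and should be reported as such.
- Control multiplicity across these outcomes by Holm. This is required, because it replaces the multivariate gate of Item 17. Amend Item 17 to match.
- Keep weeks 4-20 as a supportive trajectory, with means and CIs by arm, so that temporal and harm monitoring is retained.
- Leave liking out of the tests: Table 2 collects it as open-ended text.

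The cost is SAP wording only; no data collection changes. The downside is that comparisons between intermediate visits carry no confirmatory p-value.
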